2.2.4 RATIONALE FOR USE OF CD24FC TO REDUCE LDL

During Oncolmmune's Phase I trial, serum samples were taken and the level of LDL was measured over time; the 240mg dose significantly reduced LDL (see Figure) and IB section 2.4.2 for more information).

CD24Fc has also been used in Phase II testing for the prophylaxis of acute GVHD in cancer patients undergoing allogeneic myeloablative hematopoietic stem cell transplantation (HCT). In the Phase IIa portion of the trial (ClinicalTrials.gov Identifier: NCT02663622), patients were sequentially double-blind randomized into three cohorts with 2 placebo

and 6 in CD24Fc treatment. The two single ascending dose cohorts (240 mg and 480 mg) and one multidose cohort (480 mg (day -1), 240 mg (day +14) and 240 mg (day +28)) were given CD24Fc in addition to standard of care GVHD prophylaxis with tacrolimus and methotrexate. The LDL levels were examined and recorded at pre-dosing baseline and Day 14 post-HCT. The D14 samples in the multi-dose cohort were taken before the D14 CD24Fc administration. The D14 results in the multi-dose cohort are combined with the 480mg single dose cohort as both groups of patients received 480mg at Day-1. In this Phase IIa clinical trial, HCT patients underwent myeloablative conditioning treatment with intensive chemotherapy before the HCT. Some patients had additional total body irradiation. The placebo group had an average 78+19% of the D14 LDL level to the pre-dosing level. The CD24Fc 240mg group had an average of 50+10% of the D14 LDL level to the pre-dosing level. The CD24Fc 480mg group (including the single dosing and multi-dosing groups) had an average of 60+20% of the D14 LDL level to the pre-dosing level. When compared with placebo control, both 240mg and 480mg of CD24Fc significantly reduced LDL-C at Day 14 post-HCT. These results suggest that LDL is significantly reduced with use of CD24Fc; this investigation aims to see if a similar reduction occurs in HIV positive patients who are virally suppressed, thus serving as a surrogate marker for CVD risk reduction. For more information, please see section 2.4.2 of the IB.

2.3 RISK/BENEFIT ASSESSMENT

2.3.1 KNOWN POTENTIAL RISKS

To date, CD24Fc has been tested in a Phase I clinical study in healthy subjects, and in a Phase IIa trial for the prevention of acute GvHD following myeloablative allogeneic HSCT.

Phase I Study: The Phase I study was a randomized, double-blind, placebo-controlled, single ascending dose study to assess the safety, tolerability, and PK of CD24Fc in healthy male and female adult subjects. A total of 40 subjects in 5 cohorts of 8 subjects each were enrolled in this study. Six of the 8 subjects in

each cohort received study drug and 2 subjects received placebo (0.9% sodium chloride, saline). The first cohort was dosed with 10 mg and succeeding cohorts received 30 mg, 60 mg, 120 mg, and 240 mg of CD24Fc or matching placebo and were dosed at least 3 weeks apart to allow for review of safety and tolerability data for each prior cohort.

The Phase I study showed that the single dose of CD24Fc up to 240 mg by IV administration was generally well tolerated in healthy subjects. The most common TEAEs reported by subjects included headache and second-degree burns. However, no statistically significant difference was observed between those who received placebo vs those who received CD24Fc. All TEAEs in the study were considered mild or moderate in severity by the Investigator except for 1 subject in the placebo group who experienced a severe headache. A drug-related SAE of ventricular tachycardia was experienced by 1 subject in the CD24Fc 60 mg group. The SAE was considered mild in severity by the Investigator and did not lead to discontinuation from the study, and occurred at a rate comparable with normal populations, was considered mild by the Investigator, and did not lead to discontinuation from the study. There were no infusion reactions or injection site reactions reported.

Phase II study: The Phase IIa GvHD study was also a randomized, double-blind, placebo-controlled trial that evaluated the safety and tolerability of the addition of CD24Fc to standard GVHD prophylaxis in healthy male and female adult subjects in subjects undergoing myeloablative allogeneic hematopoietic cell transplantation (HCT). The Phase IIa trial comprised two single ascending dose cohorts (240 mg and 480 mg) and a single multi-dose cohort (480/240/240 mg)of CD24Fc to define the recommended phase IIb dose (RP2D) or maximum tolerated dose (MTD). A total of 24 subjects in 3 cohorts of 8 subjects were enrolled in this study. Six of the 8 subjects in each cohort received study drug and 2 subjects received placebo (0.9% sodium chloride, saline).

The safety profile of CD24Fc did not appear to be affected by increasing dose or multiple administrations. No patients experienced a DLT during the study. The MTD was not reached. One patient in the 480 mg CD24Fc single dose cohort and 2 patients who received placebo experienced a study drug-related TEAE. The most common study drug-related TEAE was diarrhea. No patients in other cohorts experienced a study drug related TEAE. The highest dose in this study, 960 mg CD24Fc multiple dose (ie, 480 mg, 240 mg, and 240 mg on Days -1, 14, and 28, respectively), is considered safe and recommended for future studies. The most common adverse events (AEs) observed included hematologic AEs (i.e. anemia, thrombocytopenia, leukopenia, neutropenia), nausea and oral mucositis, which are expected based on the patient population and/or treatment procedure.

As with the FIH study and the Phase II GvHD study, the planned studies include many precautions that are being taken to ensure subject safety. The protocol has been designed to exclude subjects who are at heightened risk of adverse events (AE) and ensure that clinical sites are equipped to manage any toxicities.

Based on the known biology of the CD24-Siglec pathways and its importance in the immune system, immune-related adverse events (irAE) are the most likely class of toxicity that could be observed in humans. As in the FIH and Phase IIs GvHD study, potential risks, and plans to mitigate these risks are incorporated into the design of future studies.

Ventricular Tachycardia: An SAE of ventricular tachycardia was observed in one healthy subject that received CD24Fc in the Phase 1 trial. This SAE was considered mild in severity by the investigator and did not lead to discontinuation of the subject from the study. This SAE was considered to be drug related due to its close temporal proximity to dosing, though similar short, isolated episodes of non-sustained ventricular tachycardia may be seen in up to 4% of normal, healthy populations. No deaths or adverse events leading to discontinuation occurred during the study.

During the Phase IIa trial, all patients had 12-line EKG before and after each CD24Fc or placebo I.V. infusion. The 24 patients in Phase IIa trial did not have abnormal EKG when compared with baseline predosing EKG.

Based on the mechanism of action and pre-clinical data, there is no reason to believe that CD24Fc administration would lead to ventricular tachycardia or any other cardiac-related adverse events. Inclusion criteria for the CD24Fc in preventing GVHD study includes having a Hematopoietic Cell Transplant-Co-morbidity Index (HCT-CI) of \leq 4, which includes an assessment of arrhythmia and cardiac co-morbidities. Vital signs will be monitored before and during each infusion of CD24Fc in this trial, and an assessment of arrhythmia and cardiac co-morbidities will be done in the screening period.

Adverse Immune Suppression: Preclinical studies indicate that CD24Fc is not broadly immunosuppressive. Preclinical data have demonstrated that CD24 negatively regulates host inflammatory response to cellular Danger-Associated Molecular Patterns (DAMPs) that are released as a result of tissue injury and, through interaction with its receptor, Siglec G, CD24 provides a powerful negative regulation for host response to tissue injuries. This mechanism is particularly relevant to the lead indication, GVHD and extensive preclinical studies have demonstrated that CD24Fc prevents GVHD in a mouse model. Tissue injury is caused by hematopoietic stem cell transplantation conditioning regimens, including high-dose chemotherapy and/or total body irradiation (TBI), and is considered to be the first step in the development of acute GVHD. In contrast, host response to pathogen-associated molecular patterns (PAMPs) is unaffected by CD24-Siglec G interaction and thus the CD24-Siglec G interaction appears to play a critical role in discriminating DAMPs from PAMPs.

Importantly, the drug has advantages over conventional immunosuppressants as it does not cause general immune suppression and use of high doses of CD24Fc does not block antibody response in non-human primates. Furthermore, an important function of allogeneic stem cell transplantation is to use donor T cells to eliminate allogeneic leukemia cells. This effect is called GVL. Importantly, treatment of CD24Fc, which prevented GVHD had no effect of GVL in the mouse model. Finally, extensive studies in non-human primate demonstrate that CD24Fc does not suppress antigen-specific immune response, which suggest that CD24Fc will not likely increase risk of infection. Regardless, eligibility criteria in this study excludes subjects that are considered at risk for uncontrolled infections. Serum samples will be evaluated for autoantibodies as indicated in the SOA. In the Phase IIa trial, the rate of fungal, bacterial and viral infections was not significantly increased. Instead, there seemed to be a trend of reduced CMV reactivation.

In this trial, HIV patients with anti-retroviral treatment may have increased risk of infections. However, the eligibility criteria in the planned study exclude subjects that are considered at risk for uncontrolled infections.

Infusion Reactions: Infusion reactions have not been observed in the Phase 1 or Phase IIa clinical trials. However, the administration of any recombinant protein has the potential to elicit infusion reactions. CD24Fc includes the Fc portion of human IgG1. After target binding, CD24Fc may induce FcγR crosslinking, which has been associated with infusion reactions for some therapeutics.

Infusion reactions may include events such as changes in vital signs, fever, difficulty breathing, hypotension, generalized or facial edema, nausea, chills, mental status changes, urticaria or vomiting during or up to 2 hours following infusion. The Phase IIa Clinical Protocol incorporated generalized procedures designed to closely monitor, minimize and manage any potential infusion reactions and initially was administered only on an inpatient hospital unit. However, the protocol was amended to allow CD24Fc dosing to be administrated in outpatient clinics for the multi-dosing cohort of 8 patients.

in this study, patients will be monitored before, during, and for 2 hours post infusion to assess for infusion-related reactions.

Exacerbation of Immune Responses:

CD24 has wide-spread expression among both hematopoietic and non-hematopoietic cells and, as a rule, CD24 tends to express at higher levels among immature immune cells than their terminally differentiated products. Therefore, CD24 has been widely used as a marker to track the development of both T and B cells.

CD24 was initially identified as a costimulatory molecule on activated B cells by functional screening for monoclonal antibodies that inhibit T cell activation driven by activated B cells. One of the most potent antibodies was identified as recognizing CD24 on B cells. When expressed on CHO cells, CD24 can provide costimulatory activity for clonal expansion of naïve CD4 T cells. Enk and Katz demonstrated that the CD24 functions as a costimulatory molecule on Langerhans cells (Enk and Katz 1994) ¹⁹, as anti-CD24 blocks proliferation and induces clonal anergy of cloned Th1 cells. The function of CD24 in CD8 T cell priming was demonstrated in two models. First, CD24 was rapidly induced on macrophages following the phagocytosis of latex beads (De Bruijn et al 1996)²⁰. The induction of CD24 was essential for the *in vitro* priming of naïve CD8 T cells, as such priming was completely abrogated by anti-CD24 antibodies. Second, transfection of CD24 into tumor cells resulted in enhanced priming of CD8 T cells *in vivo* (Want et al 1987)²¹. These results demonstrated that CD24 is a costimulatory molecule capable of promoting the priming of both CD4 and CD8 T cells. Therefore, there is a theoretical risk that CD24Fc could exacerbate immune responses.

Pre-clinical animal models of disease, including GVHD, did not show any exacerbation of immune responses. Clinical observations during the FIH study did not suggest an exacerbation of immune responses. The Phase IIa clinical trial provided evidence that CD24Fc suppresses the severe acute GVHD while preserving the graft vs leukemia effect. There was no increase of infection in this highly susceptible population. In the planned trial, serum samples will be collected evaluated for anti-drug antibodies, and the eligibility criteria exclude those that are at high risk for uncontrolled infections.

Other Risks:

The primary risks of phlebotomy include occasional bleeding or bruising of the skin at the site of needle puncture, and the sensation of transient lightheadedness, or rarely, fainting and infection. The amount of blood drawn will be within the limits allowed for adult subjects.

The risks of intravenous catheters used to give the study drug or placebo includes local bleeding, infection, or local inflammation of the skin and vein with pain and swelling.

After the ECG, subjects may experience mild skin irritation, slight redness or itching where the recording patches were placed. They may also need to have chest hair shaved for the procedure.

The risks with transient elastography are minimal since it is a non-invasive procedure. Patients may feel discomfort from the cold temperature of the gel that is applied for sonography, or from the pressure the probe transducer elicits against the skin with sound wave.

The study involves exposure to radiation from the radioactive sugar, but the radiation from 2 FDG PET/CT scans will be less than the radiation safety limit for research. There is no medical risk from lying in the scanner, although subjects may become uncomfortable or restless. Subjects will also have to fast 6 hours before the appointment due to the use of radioactive glucose, which may also cause discomfort.

In addition to any radiation concern, there could be psychological distress caused by an incidental finding of asymmetric FDG uptake that would likely necessitate additional investigation to exclude cancer. Additional minimal risks include bleeding or bruising at the venous site of FDG administration.

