Overall, treatment with CD24Fc resulted in trends toward a higher Grade III to IV acute GFS rate at Day 180 (94.4% and 50.0%, respectively) (hazard ratio = 0.1), higher DFS rate at 1 year post-HCT (83.3% and 50.0%, respectively) (hazard ratio = 0.2), better OS rate at 1 year post-HCT (83.3% and 50.0%, respectively) (hazard ratio = 0.2), and higher Grade III to IV acute GFS and relapse-free survival (GRFS) rate at Day 180 (83.3% and 33.3%, respectively) (hazard ratio = 0.2) compared to placebo.

Additionally, there were overall trends toward a lower cumulative incidence rate of relapse at 1 year post-HCT (11.1% and 33.3%, respectively) (hazard ratio = 0.3) and a lower cumulative incidence rate of TRM at Day 180 (0.0% and 16.7%, respectively) and 1 year (5.6% and 16.7%, respectively) (hazard ratio = 0.3) for the CD24Fc treatment group compared to the placebo group.

Overall, there was a trend toward a lower incidence of Grade III to IV acute GVHD by Day 180 in CD24Fctreated patients when compared to patients receiving placebo (5.6% and 33.3%, respectively) (hazard ratio = 0.1) but a higher cumulative incidence of Grade II to IV acute GVHD by Day 100 for the CD24Fc treatment group compared to the placebo group (38.9% and 16.7%, respectively) (hazard ratio = 2.6). Overall, the Grade II to IV acute GFS rate at Day 180 was slightly higher in the CD24Fc treatment group compared to the placebo group (61.1% and 50.0%, respectively).

Overall, there was a trend toward a higher incidence of chronic GVHD at 1 year post-HCT in CD24Fctreated patients when compared to patients receiving placebo (63.3% and 33.3%, respectively) (hazard ratio = 2.1) and a similar GRFS rate at 1 year post-HCT (32.4% and 33.3%, respectively) (hazard ratio = 0.7).

In total, 13 (72.2%) patients who received CD24Fc and 2 (33.3%) patients who received placebo had an infection through Day 100. The majority of the infections were bacterial or viral and occurred in the blood or urine. The majority of the bacteria recovered from blood culture were common skin inhabitants and low virulence pathogens (i.e., coagulase negative staphylococci).

CALIBER OncoImmune CD24Fc-003 Protocol HP-00086029

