In total, 1 (4.2%) patient died during the study due to TEAEs. Patient received placebo and experienced Grade 4 pneumomediastinum and Grade 5 pneumonia TEAEs that resulted in death. Per the Investigator, it was considered unlikely that these TEAEs were related to study drug.

In total, 9 (37.5%) patients experienced a treatment-emergent serious adverse event (SAE): 2 (33.3%) patients in the 240 mg CD24Fc single dose cohort, 1 (16.7%) patient in the 480 mg CD24Fc single dose cohort, 4 (66.7%) patients in the 960 mg CD24Fc multiple dose cohort, and 2 (33.3%) patients who received placebo. Treatment-emergent SAEs reported for patients who received CD24Fc were nausea, stomatitis, abdominal pain, dehydration, decreased appetite, device related infection, arthritis, polymyalgia rheumatica, weight decrease, cognitive disorder, and pulmonary embolism.

No patients experienced a study drug-related treatment-emergent SAE.

In total, the incidence of TEAEs of alanine aminotransferase increase and blood alkaline phosphatase increase were similar between patients who received CD24Fc and patients who received placebo. The incidence of TEAEs of aspartate aminotransferase increase was higher for patients who received CD24Fc compared to patients who received placebo. Treatment-emergent adverse events of blood cholesterol increase were only reported by patients in the 960 mg CD24Fc multiple dose cohort (2 [33.3%] patients). Treatment-emergent adverse events of blood creatinine increase were only reported by patients who received placebo do creatinine increase were only reported by patients who received placebo (2 [33.3%] patients). A TEAE of blood bilirubin increased was reported by 1 (16.7%) patient who received placebo.

In total, the incidence of TEAEs of white blood cell count decrease, lymphocyte count decrease, and neutrophil count decrease were higher in patients who received CD24Fc compared to patients who received placebo. The incidence of TEAEs of platelet count decrease was similar between patients who received CD24Fc and patients who received placebo.

No patient had a laboratory abnormality that was considered an SAE or resulted in discontinuation of study drug.

No patients who received either single or multiple dosing of CD24Fc had positive ADA results at any time point sampled pre- or post-infusion.

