- There was a trend toward a higher cumulative incidence of Grade II to IV acute GVHD by Day 100 for the CD24Fc treatment group compared to the placebo group (hazard ratio = 2.6).
- The Grade II to IV acute GFS rate at Day 180 was slightly higher in the CD24Fc treatment group compared to the placebo group.
- Treatment with CD24Fc resulted in a trend toward a lower cumulative incidence rate of relapse at 1 year post-HCT compared to treatment with placebo (hazard ratio = 0.3).
- There was a lower rate of CMV reactivation among the at risk populations but a higher rate of infection with CD24Fc treatment compared to placebo.
- The majority of the bacteria recovered from blood culture were common skin inhabitants and low virulence pathogens.
- Multiple doses of CD24Fc induced more sustained exposure over time and resulted in higher mean plasma CD24Fc concentrations on Day 100 compared to the single dose cohorts.
- The median $t_{max,-1d}$ and $t_{max,28d}$ remained consistent across all of the CD24Fc doses.

CALIBER OncoImmune CD24Fc-003 Protocol HP-00086029

[figure not shown]
• No patients who received either single or multiple dosing of CD24Fc had positive ADA results at any time point sampled pre- or post-infusion.

For more information, please see section 5.2 of the IB.

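### Section 2.3.1 says infections did not increase in Phase IIa, although section 2.2.3 reports 13/18 versus 2/6; temperature is missing from the vital signs, and no rule requires an infusion to be deferred for infection below Grade 4

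*Combined protocol and SAP*

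**What the plan says.** **Infection risk (section 2.3.1).** The protocol accepts that "HIV patients with anti-retroviral treatment may have increased risk of infections" and answers that "the eligibility criteria in the planned study exclude subjects that are considered at risk for uncontrolled infections". Under the later sub-heading on exacerbation of immune responses it says of Phase IIa: "There was no increase of infection in this highly susceptible population". It then repeats that "the eligibility criteria exclude those that are at high risk for uncontrolled infections".

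**Phase IIa data (section 2.2.3).** "In total, 13 (72.2%) patients who received CD24Fc and 2 (33.3%) patients who received placebo had an infection through Day 100". The section's own conclusions record "a higher rate of infection with CD24Fc treatment compared to placebo". It also reports that adverse events of "white blood cell count decrease, lymphocyte count decrease, and neutrophil count decrease were higher in patients who received CD24Fc".

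**Infusion reactions (section 2.3.1).** "Infusion reactions may include events such as changes in vital signs, fever, difficulty breathing". The section promises monitoring before, during and for two hours after the infusion. Sections 6.1.2, 8.3 and 8.4.4 each define vital signs as pulse, respiratory rate, oxygen saturation and blood pressure.

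**Dosing and stopping rules.** Section 7.1 and Appendix A require an individual pause for a Grade 4 event. Section 7.1 sends Grade 3 events to the principal investigator and Medical Monitor. Sections 8.1.1.5 and 8.1.1.6 allow the Week 2 and Week 4 doses to be held for adverse events or laboratory abnormalities that warrant it, without listing any. Section 8.1.1.4 (Day 0) has no hold clause. Section 7.2 requires withdrawal for life-threatening infection, for a category C AIDS-indicator condition, and, with no grade threshold, where the investigator judges continuation to be against the participant's interest or the risk to be significant.

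**The concern.** Section 2.3.1 names infection as a risk in this population and then offers reassurance. One reassuring sentence contradicts the data that the same protocol summarises a few pages earlier. The eligibility safeguard is only partly matched by a written criterion.

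Safety is the first primary endpoint, and section 2.3.1 is the text from which an ethics committee, the DSMB and the investigators judge risk. If it reports no increase where the observed rate was about twice as high, they start from a wrong picture. The plan also promises to watch for infusion reactions, but the checks it lists would not measure one of the signs it names. Before a dose, the same missing reading would be the simplest prompt that a participant may have an acute infection. Without a named reason to defer, the handling of such a participant can differ between investigators and visits.

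**Working it through.** **1. Reproduce the reported rates.** Section 2.2.3 describes three cohorts, each with 6 CD24Fc and 2 placebo patients, so the denominators are 3 × 6 = 18 and 3 × 2 = 6.

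- CD24Fc: 13/18 = 72.2%
- Placebo: 2/6 = 33.3%

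Both match section 2.2.3. The difference is 72.2 − 33.3 = 38.9 points; the risk ratio is 0.722/0.333 = 2.17.

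**2. Uncertainty of the difference.** Wilson 95% limits are 49.1% to 87.5% for 13/18 and 9.7% to 70.0% for 2/6. Newcombe's method combines them:

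- Lower: 0.389 − √[(0.722 − 0.491)² + (0.700 − 0.333)²] = −0.044
- Upper: 0.389 + √[(0.875 − 0.722)² + (0.333 − 0.097)²] = 0.670

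The interval runs from −4.4 to +67.0 points. The log-method 95% CI for the risk ratio is 0.67 to 6.96.

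**3. Test.** With 15 infections among 24 patients, the two-sided Fisher p-value sums the tables no more likely than the observed one. For 13, 14, 15 and 9 infections on CD24Fc this gives 0.0983 + 0.0140 + 0.0006 + 0.0372 = 0.150. At the observed rates, a two-sided 5% Fisher test with 18 versus 6 patients has about 27% power, so a non-significant result says little.

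**4. Two statements in section 2.3.1 compared with the data.** Under immune suppression, the section says the infection rate was not significantly increased. That agrees with p = 0.15, though it is weak evidence. Under exacerbation of immune responses, it says there was no increase at all. That disagrees with 13/18 versus 2/6 and with the protocol's own conclusion in section 2.2.3.

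**5. White-cell counts.** Section 2.2.3 gives white-cell decreases in (6 + 6 + 5)/18 = 17/18 (94.4%) versus 4/6 (66.7%), Fisher p = 0.14. This too is a numerical excess in a small sample.

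**6. Safeguards against acute infection, side by side.**

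| Stage | Written protection | What is not written |
|---|---|---|
| Eligibility (5.1, 5.2) | CD4 ≥350, two years of viral suppression, neutrophil limit, immunosuppressant exclusion, uncontrolled hepatitis B, active hepatitis C, criteria 1a and 8 | A general acute-infection criterion |
| Day 0 (8.1.1.4) | History, examination and medication reconciliation before infusion | A hold clause |
| Weeks 2 and 4 (8.1.1.5, 8.1.1.6) | Adverse event review and a discretionary hold | Infection or fever as a reason |
| Pause and withdrawal (7.1, 7.2, Appendix A) | Grade 4 pause; withdrawal for life-threatening infection, category C condition, or best interest | A mandatory infection-specific hold below these levels |
| Vital signs (6.1.2, 8.3, 8.4.4) | Four measures | Temperature |

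**The case against.** The best defence is that the protocol leaves wide room for clinical judgement. Criterion 1a covers significant illness, including participants still under evaluation for one. Criterion 8 covers any medical condition judged a contraindication. The Day 0 history, examination and medication reconciliation would usually reveal an infection or an anti-infective drug. Section 7.2 requires withdrawal, at any grade, when continuing is against the participant's interest. The eligibility claim concerns uncontrolled infection, which the CD4, viral-load, neutrophil and immunosuppressant criteria do address. The infection argument in section 2.3.1 also draws on mechanism and primate data, and the disputed sentence sits under a different sub-heading. The vital-sign lists do not forbid taking a temperature.

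Most of this stands, and it rules out two stronger readings. A reader might infer that the trial has no protection against dosing during an infection; sections 5.2, 7.2, 8.1.1.5 and 8.1.1.6 show otherwise. A reader might also infer that CD24Fc raises infection risk. The interval includes zero, there were 6 placebo patients, and all patients had undergone myeloablative conditioning, so the data do not establish that.

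The defence does not reach three things. The sentence is contradicted by section 2.2.3. No definition of vital signs requires temperature. Below Grade 4 or life-threatening severity, deferring a dose for infection as such rests on judgement with no stated trigger.

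**Conclusion.** The point holds as a correction to the risk statement and a modest monitoring gap; it is not evidence of harm. The observed infection rates differ by 38.9 points (95% CI −4.4 to 67.0, p = 0.15), which supports neither an increase nor its absence. The calculation assumes only the denominators of 18 and 6 described in section 2.2.3. The lack of temperature and of a named infection trigger follows from reading the sections together and needs no assumption.

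How often an infection below Grade 4 would coincide with an infusion cannot be sized, because the documents give no infection rate for this population. Any probability would be an assumption and would not show that such a participant would in fact be dosed. Correcting the sentence and adding temperature are the firm recommendations. A named deferral rule is secondary, because its cut-offs are debatable.

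**What to change.** 1. **Temperature.** Add it to the vital signs in sections 6.1.2, 8.3 and 8.4.4, taken before each infusion and at the existing 30-minute checks.
2. **Risk statement.** In section 2.3.1, replace the sentence with: infection through Day 100 occurred in 13/18 (72.2%) CD24Fc and 2/6 (33.3%) placebo patients; the sample is too small to show or exclude an increase. The statement that the rate was not significantly increased can stay.
3. **Optional deferral rule.** In sections 8.1.1.4 to 8.1.1.6, name fever or an infection under systemic treatment as a reason to defer the infusion within the ±4-day window, with cut-offs set by the sponsor. State what happens if the window closes. One skipped dose leaves 2/3 = 67% of treatment, below the 80% example in the per-protocol definition (section 9.3), and section 7.2 withdraws a participant unable to receive two doses. Both need to be reconciled with the rule. Framing it as a deferral, not a new exclusion criterion, keeps a passing infection from triggering the section 7.2 withdrawal for newly met exclusions.

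The cost is one amendment, a thermometer reading at checks already scheduled, and a few deferred doses. No new visits or assays are needed.
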